The risks of exposure to TMS in pregnancy are unknown. Therefore, women of childbearing capacity who are eligible for the study will be asked to take a pregnancy test and will be required to use protection during the study. Pregnant women will be excluded.

There are no known long-term adverse effects reported with the use of rTMS. However, as this is a relatively new treatment, there may be unforeseen risks in the long-term that are currently unknown.

In summary, Most common side effects of rTMS include seizures, headache, scalp discomfort at the site of stimulation, tingling, spasms or twitching of facial muscles, lightheadedness, discomfort from noise during treatment. Less common side-effects include seizures, mania, particularly in people with bipolar disorder and hearing loss due to inadequate ear protection during treatment

If subject experiences seizures or any of the side effects develop and become intolerable, the subject will be removed from the study treatment.

Participants are at risk for injury from MRI if they have pacemakers, aneurysm clips (metal clips on the wall of a large artery) or shrapnel fragments. Welders and metal workers are also at risk for injury because of possible foreign bodies in the eye. The magnetic field in the scanner may make pacemakers or watches malfunction and may make metal objects move or be dislodged. Therefore participants will be asked to remove all metallic objects on their clothing or jewelry before entering the scanner room. If subjects become uncomfortable in the scanner, they will have an alarm system at their disposal to stop the scan immediately. They may also become frustrated or bored or claustrophobic during these scans. They can be removed from the magnet at any point in the test.

Psychological risks include: worsening of depression. The research team will monitor the subject regularly, provide twenty-four hour access, and carefully educate the subject and caregiver about these risks and about when to call the research team. Subjects will be removed from the study early if it becomes clear that the risks of continuing treatment outweigh the benefits of continuing the study.

There are risks of confidentiality regarding the results of the evaluation, which might be used to discriminate against the person. All patients' files will be kept in locked cabinets. Additional confidentiality safeguards include: use of uniquely-coded study numbers, and maintenance of separate files of statistical vs. potentially identifying information. At all times, information about participants will be kept anonymous to study personnel other than the study staff. All members of the research team will have participated in human subjects training. Procedures for the protection of human research subjects will continue to be supervised and approved by the Institutional Review Board. Information will be disclosed whenever necessary only to the FDA, IRB, or the Department of Defense (DoD)..

There are no known social, legal, or other risks at this time. If such risks become known, the research team will immediately inform all subjects.

In this research study, there is no alternative treatment other than rTMS treatment. If subjects are unable to complete the study, they will be referred to appropriate treatment centers.

Steps taken to minimize the risks: As above

Plan for reporting unanticipated problems or study deviations: Any unanticipated problems or study deviations will be reported to Hopkins IRB and the DoD.

Financial risks to the participants: There are no financial risks to the patients.

All subjects will be instructed to call if they experience any new or worsening in symptoms.

Benefits

Study benefits include free comprehensive psychiatric evaluations, sleep studies and brain scans. These results if requested by the study participants will be made available to them.

There are currently no established protocols for the treatment of post-TBI depression & comorbidities. Hence the results of this study will make a significant contribution to the TBI literature. Results from this pilot study will be used to design study with larger sample size.

If the proposed rTMS treatment is found to be efficacious, it can be transferred to clinical practice for soldiers with TBI-associated depression and other psychiatric symptoms. rTMS has minimal long-term side effects and is not known to negatively interact with pharmacotherapies. rTMS has the potential to have a broader impact on multiple areas of life functioning and, thus, has the potential to lead to improved instrumental life activities, employability, community re-integration and overall quality of life. Soldiers with increased emotional stability and improved cognitive skills can more effectively manage stress which, in turn, can dramatically reduce the probability of developing disorders associated with chronic stress.

The major strength of this study is that it will be the first study to determine the effectiveness of low frequency right-sided rTMS for the treatment of common psychiatric disturbances that often co-occur with TBI. If successful, this will be a major advancement in the treatment of TBI because rTMS, has minimal long-term side effects and is not known to negatively interact with other drugs – important factors to be considered in this medically fragile population. Other unique aspects of the proposal include: (a) the use of a treatment strategy that is not purely symptom-based but has the potential to enhance cortical reorganization, increase synaptic connectivity and enable functional rehabilitation (b) the potential to study the pathophysiologic impact of rTMS on white matter connectivity as determined by DTI and (c) the possible beneficial effect of rTMS on other TBI related problems such as pain, spasticity, gait, coordination. Finally, if the results of the clinical trial are not positive, the study will still yield novel and abundant information on the nature of TBI sleep disturbance as well as anatomical correlates of TBI related neuropsychiatric disturbances, which have potential as diagnostic and prognostic markers

8. Payment and Remuneration

Subjects will be paid \$54.00 for travel & snacks per visit.

1000.00 will be paid to each subject for their visits and treatment (\$175.00/week for each of the 4 weeks they get rTMS/sham treatment; \$75.00 for each of the 3 follow-up visits; bonus of \$75.00 at the end of study).

In addition, they will be paid \$400.00 for the overnight sleep studies (\$200.00 for pre-treatment and \$200.00 for post treatment). Subjects will have to spend 2 nights at the sleep lab, both at pre and post-treatment (total 4 nights).

The total cost per subject for 30 subjects will be \$1,400 for participation and completion of study.

Twenty five subjects will receive an additional \$50.00 for the brain scan done pre-treatment and \$50.00 for scan done post treatment. These twenty five subjects will receive \$1400.00 + \$100.00 = \$1500.00. All payments will be by cash, as we have done in our previous TBI studies.

As per the Department of Defense (DoD) rules, active duty research volunteers cannot receive any payment for participation unless they are off duty or on leave during the time they are participating in the study.

9. Costs

The cost of treatment (rTMs or Sham) is \$70.00 per treatment.

The cost for MRI 3T scanner for an hour of scanning = \$645.00.

The cost for 2-overnight Polysomnography = \$450.00

REFERENCES:

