Specific Aim 2: To determine the effectiveness of LFR rTMS for the treatment of neuropsychiatric symptoms that are commonly seen as co-morbid phenomena in patients with post-TBI depression: (a) post traumatic stress disorder (PTSD) (b) sleep disturbance and (c) cognitive deficits. We hypothesize that LFR rTMS will be superior to sham treatment in reducing symptoms of PTSD, sleep disturbance and cognitive deficits, more specifically, memory, attention and executive function deficits. In addition, effectiveness of rTMS for the treatment of other behavioral symptoms (e.g. apathy, aggression) will be assessed.

Exploratory Analysis: A subset of subjects will be assessed using diffusion tensor imaging (DTI) to determine white matter integrity pre- and post-treatment in an effort to better understand neuro-anatomical correlates of NPS symptoms, symptom improvement, and the potential for LFR rTMS to influence white matter integrity.

Study Design: The study design will include a double-blind placebo-controlled trial of 30 TBI patients of mild & moderate severities. Subjects will be randomized to either active LFR rTMS (N=15) or sham treatment (N=15). All subjects will receive 20 LFR rTMS or sham treatments over 4 weeks, and will be followed thereafter for 3 months. Well-validated psychiatric instruments and cognitive assessments will be

used to compare the effectiveness of LFR rTMS versus sham treatment cross-sectionally at each of the visits and over time.

Relevance: If the proposed rTMS treatment is found to be efficacious, it can be transferred to clinical practice for soldiers with TBI-associated depression and other psychiatric symptoms. rTMS has minimal long-term side effects and is not known to negatively interact with pharmacotherapies. rTMS has the potential to have a broad impact on multiple areas of life functioning and, thus, has the potential to lead to improved instrumental life activities, employability, community re-integration and overall quality of life. Soldiers & civilians with increased emotional stability and improved cognitive skills can more effectively manage stress which, in turn, can dramatically reduce the likelihood of developing disorders associated with chronic stress.

2. Objectives

The overarching goal of this proposed proof of concept study is to determine the effectiveness of low frequency right (LFR) rTMS for the treatment of post-TBI depression and co-morbid psychiatric symptoms.

SPECIFIC AIMS & HYPOTHESES

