Study Design: We propose a double-blind placebo controlled proof of concept pilot study of active versus sham LFR rTMS for the treatment of TBI depression. As noted above, all subjects will be screened prior to randomization. During the screening visit, all subjects will undergo a complete psychiatric evaluation as well as formal cognitive testing. In addition, if there is any possibility of pregnancy or unstable medical status, the PI or physician co-investigator will ask the potential subject's treating psychiatrist or primary care physician (PCP) to conduct a urine pregnancy test and/or bloodwork to rule out infections and liver, kidney or thyroid abnormalities. If the potential participant does not have a PCP or psychiatrist, a lab requisition will be provided to the participant. He/she will be considered for the study only after the lab results are reviewed by the study physician and found to be normal. .

Subjects will be randomized using a custom in-house software method, and will be stratified on time since injury: <5 years post injury versus ≥ 5 years.

All members of the research team will be blind to individual subjects' treatment condition, with the exception of the rTMS staff member, [name]. The success of subject blinding will be evaluated by asking subjects, during the first and last week of treatment, whether they believe that they received active or sham rTMS treatment. The rTMS technician will ask this question and note down the answer in the weekly assessment form.

Study Treatment: Subjects will receive either LFR rTMS or sham treatment.

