There is no Food and Drug Administration (FDA) approved drug for the treatment of TBI-related NPS symptoms/syndromes. There are only two controlled medication trials in TBI-associated depression, and neither provided strong evidence that antidepressants are superior to placebo. A major limitation of previous studies has been their focus on limited symptoms and use of agents with narrow therapeutic profiles. We propose to address some of these limitations by use of a novel non-invasive technique, LFR rTMS, that has the potential to induce widespread neuromodulation.

Justification and safety information if FDA approved drugs will be administered for non-FDA approved indications or if doses or routes of administration or participant populations are changed. NA

Justification and safety information if non-FDA approved drugs without an IND will be administered. NA. We anticipate that the Johns Hopkins IRB will classify our trial as significant risk, in which case we will require an IDE from the FDA.

6. Study Statistics

General Description

- a. Definition and selection of dataset: Intention-to-treat (ITT) will include all subjects who are randomized to participate in the protocol. The per-protocol (PP) population will include all subjects in the ITT population who meet the additional criteria of no major protocol violations and compliance with study treatment. Baseline demographic and clinical features, including medical comorbidity, pain, fatigue, and post-concussive symptoms will be included in the ITT dataset. Effect assessment will be included in both the ITT and PP dataset.
- b. Basic exploratory analyses will first be conducted, including checking of distributional assumptions, assessment of relationships among covariates, and missing-value multiple imputations.
- c. Continuous variables will be described using means, standard deviations, medians, minimums and maximums, and 95% confidence intervals for parameter estimation. Graphical display (spaghetti plots) of the outcome scores will also be generated for 5 visits (baseline, end of 20 LFR rTMS sessions, week 8,12, and 16) by group. Category and count variables will be described using frequency or proportions.
- d. Analyses will be conducted using STATA 11.2 (StataCorp, Texas, 2009) or R 2.13.2 (2011). All statistical tests will be judged for significance based upon a two-sided p-value of less than 0.05.

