Treatment response: The Clinical Global Impression (CGI)^{98,99} scales are used to rate the severity of illness and assess response to treatment. CGI-Severity scale (CGI-S) is used to assess the severity of illness and CGI – Improvement scale (CGI-I) is used to assess treatment response in psychiatric patients. Both are 7-items scale. The CGI-S ranges from 1= normal to 7 = extremely ill.. The CGI-I rates participants improvement from baseline: 1=very much improved; 7=very much worse.

Primary Efficacy Measures: Changes in HAMD, PHQ9 and BSS;

Statistical Analysis

- a. All subjects will be tracked over the study period in order to capture (1) the number subjects randomized to each group; (2) the number of subjects who drop-out or are lost to follow-up, and (3) the compliance of each subject across the study period.
- b. Baseline balance analyses: At baseline, the two groups (Experimental and Control) will be compared on demographic and clinical features, including medical comorbidity, pain, fatigue and post concussive symptoms.
- c. Effectiveness analyses: Random effects models will be used to evaluate the efficacy of the intervention as assessed by HAMD and PHQ9 with comparison of the slopes of the rTMS (Experimental) and sham treatment groups (Control). Random effects models will also be used to compare the two groups over time, controlling for baseline variables found to be statistically significant between the two groups, and the coefficient of interest, such as the interaction between time and treatment assignment. Similar analysis will be done for the CGI-I and BSS scores.

In addition, remission rates (as defined by HAMD score ≤ 7 or PHQ9 = 0) and Improvement rates (as defined by CGI-I scores ≤ 2) between the two groups will be calculated using Fischer's Exact test.

Secondary Objective: To determine the effectiveness of LFR rTMS for the treatment of common co-morbid neuropsychiatric symptoms: (a) Post traumatic stress disorder (PTSD) (b) Sleep disturbance and (c) Cognitive deficits.

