Neuropsychological Tests: All subjects will complete neuropsychological testing at two time points: during the baseline visit and at the 3-month follow-up visit. The test battery will be constructed to allow evaluation of multiple domains of cognitive functioning, including global cognitive functioning, executive functioning, attention, and memory (Table 6). Briefly, the raw scores on all cognitive measures will be converted to scaled scores using the cumulative frequency distribution of each measure. Scaled scores will then be regressed on age, gender, race, years of education, and estimated premorbid IQ based on the revised National Adult Reading Test (NART)^{105,106} . No additional control for education is necessary.

Table 6: Neuropsychological Tests

Montreal Cognitive Assessment	Test of global cognitive functioning
Wechsler Test of Adult Reading (WTAR)	Pre-morbid Intelligence
Trails B	Test of Executive functioning
Controlled Oral Word Association Test (COWAT)	Test of Executive functioning
Wisconsin Card Sorting test (WCST)	Test of Executive Functioning
Stroop Test	Test of Executive Functioning
Brief test of Attention (BTA)	Test of auditory attention
Trails A	Test of visual attention
Hopkins Verbal learning test (HVLT)	Verbal Memory Test
Brief Visual Memory Test (BVMT)	Visual Memory Test

Behavior Problems: The Neurobehavioral Rating Scale—Revised (NBRs-R) will be used to measure behavioral disturbances following TBI. The NBRs-R is a clinician-based multidimensional instrument and has been validated as a secondary outcome measure to assess behavior problems after brain injury¹⁰⁷.

Secondary Efficacy Measures: DTS; PSQI, EPS, PSG and cognitive measures.

Statistical Analysis: Analyses will be similar to Aim1. Random effects model will be used to compare of the slopes of the LFR rTMS (Experimental group) versus the sham treatment group (Control group) on the Davidson Trauma Scale scores. Random effects models will also be used to compare the two groups over time, controlling for baseline variables found to be statistically significant between the two groups, and the coefficients of interest, such as the interaction between time and treatment assignment.

This same statistical analysis approach will be used to compare the two groups on the sleep scales (PSQI & EPS) and on the primary PSG sleep variables, global cognitive functioning and memory, attention and executive functioning.

Exploratory Analyses:

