Fatigue: The Fatigue Severity Scale¹¹¹ will be used to assess the severity of fatigue. It has been used both clinically and for research applications, and has been used in the assessment of fatigue in neurological and non-neurological conditions.

Post-Concussive Symptoms: As a myriad of post-concussive symptoms are present after TBI, the Rivermead Postconcussive Questionnaire¹¹² will be used to determine post-concussive symptoms and calculate the total score.

Power Analysis:

The power calculation for this study is based on the study by Fann et al⁴⁵ and our clinical experience. In the open labeled study of sertraline (Zoloft) for the treatment of TBI depression, Fann et al found a response rate (decrease in Hamilton depression scale score of > or = 50%) of 87% and remission rate (Hamilton depression scale score of < or = 7 at the end of treatment) of 67%. Based on these results, we hypothesize improvement in symptoms on the HAMD of 60-70% in the experimental group; and based on our clinical experience, we hypothesize a remission rate of 10% in the Control group. The table (Table 7) below depicts sample sizes for these remission rates with various degrees of power. As this is a pilot study, we have chosen a sample size (N=30) that is feasible and that will allow us to complete the study in the allocated time. Results from this study will help us to develop future studies with larger sample sizes and more conservative numbers. Sample size was calculated with (StataCorp, Texas, 2009) alpha was set at 0.05.

Table 7: Calculation of Sample Size.

Power	Remission rate in Experimental group (control group is 0.1)	N1 (Experimental group)	N2 (control group)	N (total)
0.9	0.7	15	15	30
0.8	0.7	13	13	26
0.75	0.7	12	12	24
0.7	0.7	11	11	22
0.6	0.7	10	10	20
0.9	0.6	21	21	42
0.8	0.6	17	17	34
0.75	0.6	16	16	32
0.7	0.6	15	15	30
0.6	0.6	13	13	26

Safety and tolerability: The following safety measures will be used:

- 1) Collection of vital signs
- 2) Collection of adverse events/side effects. All adverse events including minor rTMS side-effects like post-treatment headache as well as serious and unexpected adverse events like seizure will be recorded. All participants will be encouraged to call or page the PI if they notice any adverse effect or if they are concerned about any medical issues. Side effects will be monitored at each treatment and office visit.

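### Randomisation is stratified on time since injury, but no analysis prespecifies that factor; precision may be forgone if it is prognostic

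*Combined protocol and SAP*

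**What the plan says.** In section 4 (Study Procedures, Study Design) allocation "will be stratified on time since injury: <5 years post injury" versus 5 years or more. On method, the text says only: "Subjects will be randomized using a custom in-house software method". No block size or other balancing device within strata is given.

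In section 6 (Study Statistics), item c of the primary Statistical Analysis uses random effects models "with comparison of the slopes of the rTMS (Experimental) and sham treatment groups (Control"). It then compares the groups over time, with time-by-treatment as an example of the coefficient of interest. Adjustment is limited to baseline variables on which the arms differ significantly. Remission and improvement rates are compared by an unstratified Fisher exact test. The secondary analysis follows the same pattern: "Random effects model will be used to compare of the slopes of the LFR rTMS (Experimental group") against sham, with the same covariate rule. The Other Scales paragraph adds medical comorbidity, pain, fatigue and post-concussive symptoms as variables to be controlled. Time since injury appears in none of these places.

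In the Power Analysis, "we have chosen a sample size (N=30) that is feasible". Tests are judged on a "two-sided p-value of less than 0.05" (General Description, item d).

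**The concern.** A factor used to constrain allocation normally belongs in the analysis. If it predicts outcome and the arms are balanced on it, the treatment estimate varies less from trial to trial than an unadjusted standard error implies. The test then rejects too rarely under the null, confidence intervals are too wide, and some real effects are missed. With 30 patients, precision is scarce.

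The covariate rule makes the gap hard to close by accident. It selects variables on which the arms differ, and stratification exists to prevent such a difference. The rule could admit the factor in principle, but it cannot be relied on to do so.

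**Working it through.** **1. The plan's own figure.** Table 7 gives 15 per arm for remission of 0.7 vs 0.1 at 0.90 power. With two-sided alpha 0.05 and mean rate 0.4:

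n = [1.960·√(2·0.4·0.6) + 1.2816·√(0.21 + 0.09)]² / 0.6² = 11.79

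With continuity correction: n/4 · [1 + √(1 + 4/(n·0.6))]² = 14.93, so 15. All ten rows of Table 7 reproduce this way. No stratum enters the formula, so the planned power contains no gain from stratification. Exact power of the planned Fisher test at 15 per arm is 0.894 for 0.7 vs 0.1 and 0.739 for 0.6 vs 0.1, against 0.90 and 0.70 in the table.

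**2. Can the covariate rule admit the stratum?** Assume 30 patients, two roughly equal strata, and permuted blocks of 2, 4 or 6. In 4,000 simulated allocations for each block size, the stratum never differed between arms at p<0.05. The smallest Fisher p-values were 1.0, 0.71 and 0.44.

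**3. Between-arm comparison of a continuous score, balanced within strata.** Assumptions: strata of 16 and 14, each split equally between arms; within-stratum SD 1; stratum difference δ; complete data; no other covariates. Leaving the stratum out moves its sum of squares, with expectation 1 + 30·(16/30)·(14/30)·δ² = 1 + 7.467δ², into the residual. The expected residual mean square is then

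(27 + 1 + 7.467δ²)/28 = 1 + 0.2667δ²

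The standard error is too large by the factor √(1 + 0.2667δ²). Simulation (8,000 to 20,000 trials per setting; true effect 1.06 within-stratum SD for power) agrees:

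| δ | Formula ratio | Mean SE, unadjusted vs adjusted | Type I error, unadjusted | Power, unadjusted vs adjusted |
|---|---|---|---|---|
| 0.5 | 1.03 | 0.373 vs 0.362 | 0.042–0.046 | 0.78–0.79 vs about 0.80 |
| 0.8 | 1.08 | 0.391 vs 0.362 | 0.035 | 0.75–0.76 vs about 0.80 |
| 1.0 | 1.13 | 0.407 vs 0.362 | 0.028–0.029 | 0.72–0.73 vs about 0.80 |

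From the simulated standard errors the excess is 3%, 8% and 12% (0.373/0.362, 0.391/0.362, 0.407/0.362). Adjusted type I error is about 0.05 throughout. At δ = 0 power is about 0.80 either way, so adjustment costs essentially nothing.

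**4. The same comparison with total SD held fixed.** Here R² is the share of outcome variance due to the stratum, and the effect is 1.06 total SD. Unadjusted vs adjusted power is 0.80 vs 0.80 at R² = 0, 0.80 vs 0.82 at 0.05, 0.81 vs 0.84 at 0.10, and 0.82 vs 0.88 at 0.20. A δ of 1.0 corresponds to R² = 0.2489/1.2489 = 0.20, where 0.2489 = (16/30)·(14/30).

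**5. No balance within strata.** At R² = 0.20 the mean unadjusted standard error is 0.363, against an actual SD of the estimate of 0.368, and type I error is 0.052. The unadjusted standard error is valid. Adjustment still adds power.

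**6. Slopes.** With complete, balanced visits, a constant shift in a patient's level does not change that patient's slope. A stratum main effect therefore leaves the time-by-treatment standard error alone: 0.3905 vs 0.3905 in random-intercept fits. In one assumed case where the stratum did change the slope, fitting stratum-by-time lowered the standard error from 0.525 to 0.484. That figure is illustrative only: it rests on 60 fits per setting, and some fits gave convergence warnings.

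**7. Remission.** Exact enumeration with strata of 8+8 and 7+7. If remission is 0.75 vs 0.15 in one stratum and 0.45 vs 0.05 in the other (assumed), Fisher power is 0.75 and a stratified exact test gives 0.80. With 0.6 vs 0.1 in both strata, the figures are 0.74 and 0.75.

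**The case against.** A reader might infer that the reported standard errors will be too large and that power bought by stratifying is lost. The documents do not support that reading, for four reasons.

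- It needs a prognostic stratum and balance within strata. The protocol gives neither a prognostic strength, nor a reason for choosing the factor, nor a blocking scheme. Stratifying on a factor does not show that it predicts outcome.
- Table 7 counted no such power. With total SD held fixed, unadjusted power stays at or above its no-stratum level of about 0.80. The drop to 0.72 in step 3 arises because stratum variance is added to a fixed within-stratum SD. What is given up is a possible further gain.
- The coefficient that the plan names is time-by-treatment, which a stratum difference in level does not touch. For slopes, the 1.0 SD case assumes a stratum effect almost as large as the 1.06 SD treatment effect.
- The clinical covariates listed under Other Scales may already absorb some of the stratum's variance. The simulations include none of them, so they may overstate the remaining gain.

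All four stand. They limit the size and certainty of the loss. They do not alter the fact that the factor is left out of every prespecified analysis, and they give no reason to omit it.

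**Conclusion.** The stratification factor is not prespecified in the random effects models or in the comparison of rates, and the covariate rule will almost never supply it. The consequence is conditional:

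- **Prognostic stratum, balanced allocation:** standard errors about 3% to 12% too large, type I error about 0.046 down to 0.029, and about 2 to 8 points of power forgone, for stratum differences of 0.5 to 1.0 within-stratum SD.
- **Prognostic stratum, allocation not balanced within strata:** the unadjusted standard error is valid, but adjustment still gains power.
- **Stratum not prognostic:** essentially no change.

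For slopes, the loss arises only if the stratum changes the rate of improvement. In no case is the effect estimate biased, and any error in the test is conservative. This is a free improvement of minor to moderate severity. The omission is clear from the text; confidence in the size of the gain is only moderate, because the prognostic strength, the split between strata (16/14) and the blocking are all assumed.

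**What to change.** In section 6, add to item c of the primary Statistical Analysis and to the secondary Statistical Analysis: *Every random effects model includes the randomisation stratum (time since injury under 5 years vs 5 years or more) and, where slopes or time-by-treatment are compared, the stratum-by-time term, whatever the baseline comparisons show. Remission and improvement rates are compared with an exact test stratified by the same factor.* A stratum main effect alone would not serve the slope comparison.

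In section 4, state how allocation is balanced within strata.

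The stratum has to be known at randomisation, so no new data are needed. The cost is one or two degrees of freedom.
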